4.2 Missing Data

For patients who do not attend the assessment, the mean imputation of the assessment scores from their allocation group has been used.

5. Informed Consent Forms (ICF)

Written consent will be gained from the patients with Knee osteoarthritis along with Kinesio phobia using the consent forms attached to the application.

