4.1 Primary Outcomes

The primary analyses will compare experimental vs control group guidelines on their mean and standard deviation: (i)Tampa scale, (ii) Visual Analogue Scale (VAS), (iii) Short-form McGill Pain Questionnaire (SF-MPQ-2) Comparison will be tested by using the Paired t test to find the significant difference within the intervention effects and between the two groups (Experimental control group and Experimental Group) using independent t-test. P values <0.05 has been considered statistically significant.

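### Filling missed assessments with the arm's own mean before t-testing makes standard errors too small, so once assessments are missed the P<0.05 rule is no longer a 5% test

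*SAP*

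**What the plan says.** Section 4.2 (Missing Data) consists of a single rule: "For patients who do not attend the assessment, the mean imputation of the assessment scores from their allocation group has been used". The SAP has no variance correction, multiple imputation, observed-case analysis or sensitivity analysis.

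The completed data feed the tests in section 4.1 (Primary Outcomes), which cover the Tampa scale, the VAS and the SF-MPQ-2. Within groups: "Comparison will be tested by using the Paired t test to find the significant difference within the intervention effects". The groups are compared "between the two groups (Experimental control group and Experimental Group) using independent t-test". The threshold is "P values <0.05 has been considered statistically significant". Section 4.1 does not say whether the independent t-test uses follow-up or change scores, and does not state sidedness.

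Section 3.3 (Recruitment) has all three scales measured at baseline, so a patient who misses the later assessment normally has a baseline score.

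**The concern.** Giving absent patients the mean of the attenders in their own arm leaves that mean exactly where it was. It also puts points with zero deviation into the variance and counts them in n and in the degrees of freedom. The t-test then treats invented values as data. The SD shrinks, the standard error shrinks further, and P becomes too small.

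This happens even when absence is pure chance, and it always pushes towards significance. It affects every primary test and every SD reported for the arms. A trial of ineffective interventions would be declared positive more often than the plan claims.

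The rule also ignores the absent patient's own baseline score, and it assumes that absentees did as well as attenders in their arm.

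**Working it through.** **Inputs.** From the SAP: own-arm mean imputation (4.2); paired and independent t-tests, threshold 0.05 (4.1). Assumed, because the SAP gives no figures: 5–30% missing per arm, equal in both arms, missing completely at random; a two-sided test; n = 20 to 100 per arm.

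**Nominal level.** With no missing data, 2·(1−Φ(1.96)) = 0.050, which reproduces the stated threshold.

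**Independent t-test on follow-up scores.** Let k of n patients per arm be observed, m = 1−k/n, and s the pooled SD of the observed scores.

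- Correct SE: s·√(2/k).
- SE after imputation: the sum of squares is unchanged but is divided by n−1 instead of k−1 per arm, so the SE is s·√((k−1)/(n−1))·√(2/n).
- Ratio: √(k/n)·√((k−1)/(n−1)) ≈ 1−m.
- The t statistic is therefore inflated by f = √(n/k)·√((n−1)/(k−1)).
- Actual level: 2·P(T with 2k−2 df > t(0.975; 2n−2)/f). For large n this is 2·(1−Φ(1.96·(1−m))).

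Example with n = 30, k = 24 (20% missing): f = √(30/24)·√(29/23) = 1.118 × 1.123 = 1.255, an SE ratio of 0.797. The critical value 2.002 becomes 2.002/1.255 = 1.594 on 46 df, so the level is 11.8%.

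| Missing per arm | 1.96·(1−m) | Level, large n | Level, exact, n = 30 |
|---|---|---|---|
| 0% | 1.960 | 5.0% | 5.0% |
| 5% | 1.862 | 6.3% | – |
| 10% | 1.764 | 7.8% | 7.8% |
| 20% | 1.568 | 11.7% | 11.8% |
| 30% | 1.372 | 17.0% | 17.2% |

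Sample size hardly matters. For n = 20 to 100 per arm, the exact levels are 7.8%, 11.7–11.8% and 17.1–17.3% at 10, 20 and 30% missing.

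**Simulation of all the tests.** 40,000 trials with no effect, n = 30 per arm, baseline–follow-up correlation 0.3, 0.5 and 0.7, only follow-up imputed:

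| Test | 10% missing | 20% missing | 30% missing |
|---|---|---|---|
| Independent t, follow-up | 7.8–8.0% | 11.8–11.9% | 17.0–17.4% |
| Independent t, change | 6.2–6.4% | 7.6–8.0% | 9.7–9.9% |
| Paired t, within arm | 6.1–6.3% | 7.4–7.6% | 9.4–9.9% |
| Independent t, follow-up, observed patients only | 4.9–5.2% | 5.0–5.1% | 4.8–5.3% |

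The paired and change-score tests suffer less because the absent patient's real baseline score still contributes spread.

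**Bias if absence is related to outcome.** If absentees in one arm are truly 0.5–1 SD worse than attenders and 20% of that arm is absent, the arm mean is wrong by 0.20 × 0.5 = 0.1 SD to 0.20 × 1 = 0.2 SD. This favours the experimental treatment if the absentees are in the experimental arm, and works against it if they are in the control arm.

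**The case against.** The strongest objection is that the size rests on an assumed dropout rate. The SAP gives none, and section 3.4 (Administration) describes short courses of three and four weeks, so few assessments may be missed. With none missed there is no inflation. At 5% missing the level on follow-up scores is 6.3%, which is modest. This stands as a limit on the size. It does not rescue the rule, which operates only when assessments are missed and then always errs in the same direction.

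Second, section 4.1 may intend change scores. At 20% missing the level is then 7.6–8.0% rather than about 11.8%. This also stands: the follow-up figures are the upper reading, and the change-score figures are still above 5%.

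Third, the bias is not peculiar to this rule. Own-arm imputation leaves the follow-up mean equal to the observed-case mean, so an observed-case analysis has the same bias. A mixed model or multiple imputation does not in general remove bias that depends on the unseen score. This is right, and the finding therefore rests on the standard error alone; the bias is a reason for a sensitivity analysis.

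Fourth, the SAP does not commit to confidence intervals. The fault is therefore stated for P values and SDs. Any 95% interval built from the same standard errors for follow-up scores would cover about 92%, 88% and 83% at 10, 20 and 30% missing.

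Fifth, deleting the rule and using observed cases already restores 5% under the assumptions used here. This is true, but that analysis still discards the absent patients' baseline scores.

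**Conclusion.** The concern holds. As written, sections 4.1 and 4.2 together do not give a 5% test for any of the three primary outcomes once assessments are missed. For 10–30% missing per arm, the actual level is about 8–17% on follow-up scores, 6–10% on change scores and 6–10% for the paired tests. The SDs reported for follow-up scores are too small by a factor of about √(1−m), which is 0.89 at 20% missing.

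These figures assume equal missingness in both arms, missing completely at random, and two-sided testing. The direction follows from the algebra; only the size depends on the unstated dropout rate. The point must be fixed before analysis.

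**What to change.** - Delete the mean-imputation rule in section 4.2.
- Analyse each primary outcome with a likelihood-based mixed model on all observed baseline and follow-up scores. Alternatively, use multiple imputation within group from the baseline scores of all three scales, combined with Rubin's rules. Neither was simulated here; both are standard methods that carry the uncertainty the present rule discards. If t-tests are kept, the minimum repair is to run them on observed patients only.
- State in section 4.1 whether the groups are compared on follow-up or change scores.
- Add one sensitivity analysis in which imputed scores in the experimental arm are made progressively worse, and report how far they can go before the conclusion changes.
- Report SDs on observed data only, with the number observed per arm.

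The cost is SAP wording and modest extra analysis, with no new patients or data. P values will be larger wherever assessments were missed. For the follow-up comparison at 20% missing, the observed-case t statistic is about 20% smaller than the one the present rule would give.
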